10.4 Re-Randomization Test

The robustness of the results to the use of the minimization randomization algorithm will be evaluated by performing a re-randomization test to compare overall survival between the treatment arm(s) and the control.

The re-randomization test will be performed as follows:

- The procedure will use 50,000 replications of the ITT population (all randomized subjects).
- For each replicate, a virtual sequence of treatment assignments (a virtual re-randomization schedule) will be created using the original minimization randomization algorithm based on the order in which the subjects were originally randomized into the trial and the value of their randomization stratification factors.
- For each replicate, primary survival analysis will be performed for OS.
- The re-randomization test p-values will be the fraction of replications where the log-rank p-values from the replicates are less than or equal to the corresponding p-values from the original analysis of overall survival.
- The empirical distribution function of the chi-square statistics obtained from the replicates will be plotted against the theoretical asymptotic Chi-square(1) distribution of the log-rank statistic for visual comparison to assess validity of the test procedure.

Robustness of the results will be established if the re-randomization test p-values are then found to be comparable to the corresponding p-values from the original analyses of OS, PFS assessed by IRC, and ORR assessed by IRC.

10.5 Sensitivity Analyses

Sensitivity analyses will be conducted to evaluate the robustness of efficacy results.

PFS, ORR, BRR, duration of response will be analyzed based on assessment by local investigator per RANO criteria, as supportive of the efficacy analyses with central imaging center evaluations.

An analysis of OS will be performed by fitting a Cox regression model with treatment arm and covariates identified in the references;^{4,5} i.e., performance status, tumor location, patient age, baseline steroids, tumor size and load. Treatment will be forced in the model and covariates will be selected using a stepwise procedure. Bootstrap technique will be used to estimate the posterior probability of inclusion in the Cox model. EORTC will perform the analysis with various model selection approaches.

Modified PFS is defined as the number of months from the date of randomization until the date of first progression assessed by IRC or death without receiving post anti-cancer therapy, whichever occurs first. Subjects for whom neither death nor progression have been documented will be censored on the date of the last radiological assessment if they have no post anti-cancer therapy. If a subject has other post anti-cancer therapy prior to progression or death, the data will be censored at the date of last radiological assessment prior to or on the start date of post anti-cancer therapy.

Accounting for subjects who died or progressed immediately after 2 or more consecutive missed assessments, modified efficacy endpoint of PFS to consider the date of the earliest missed radiological assessment prior to a subject's progression or death, as a date of progression, will be analyzed using the same statistical methodology as that for the secondary PFS endpoint.

For subjects with at least one measureable disease at baseline (defined as an enhancing tumor with two perpendicular diameters ≥ 10 mm), the number and percentage of subjects with objective responses will be presented using the same statistical methodology as that for the secondary ORR endpoint.

In case more than 10% are excluded from the per-protocol population, the primary efficacy analyses (both comparisons) will be performed in the per-protocol population at two-sided alpha 5%.

10.6 Subgroup Analyses

Efficacy endpoints (OS, PFS, ORR, BRR, CRR, and NDFS) will be assessed in the following subgroups on an as-stratified basis according to stratification data collected at randomization;

- Timing of relapse (< 16 weeks or ≥ 16 weeks after the first day of the last TMZ cycle)
- Region of the world (North America or Europe and Australia or Asia/other regions)
- WHO Performance status (0 or > 0)
- MGMT promoter methylation (status methylated or unmethylated)
- EGFR pathway abnormalities (abnormal or normal)

Differences between the treatment arms and the control arm (Arm 1 vs. Arm 3; Arm 2 vs. Arm 3) in time-to-event endpoints (OS, PFS, and NDFS) will be assessed by unstratified log-rank test. Kaplan-Meier curves comparing treatments will be presented in each subgroup.

For ORR, BRR, and CRR, the number and percentage of subjects with response will be reported with exact (binomial) two-sided 95% CI (CI for ORR and CRR only) in each subgroup by treatment arm. The ORR and CRR will be compared between the treatment arms over the control arm using a chi-square (Fisher's exact) test.

The hazard ratios (HRs) of the two treatment arms over the control arm and their 95% CIs will be calculated by a Cox's model with only treatment as covariate. Odds ratios (ORs) will be presented with 95% CIs. Forest plots will be presented to display these HRs and ORs. The forest plot will also contain the HR and OR for the ITT population for the purposes of visual comparing and contrasting.

11.0 Safety Analysis

11.1 General Considerations

Unless otherwise specified, safety analyses will be performed on the Safety population. No statistical comparisons will be performed between treatment arms. No p-values and CIs will be provided.

Unless specified, all summaries/analyses involving AEs will only include treatment-emergent adverse events (TEAEs). TEAEs are defined as any adverse event with onset or increase severity after the first dose of study drug (ABT-414/TMZ/lomustine) and no more than 35 days after the last dose of study drug (ABT-414/TMZ/lomustine).

AEs where the onset date is the same as the study drug start date are assumed to be treatment-emergent, unless the study drug start time and the AE start time are collected and the AE start time is prior to the study drug start time. If an incomplete onset date was collected for an AE, the AE will be assumed to be treatment-emergent unless there is evidence that confirms that the AE was not treatment-emergent (e.g., the AE end date was prior to the date of the first dose of study drug, a partial AE start date is available for which the month or year is prior to the first dose date of study drug).

Adverse events will be coded and summarized by system organ class and preferred term according to the Medical Dictionary for Regulatory Activities (MedDRA) version 19.0 or higher. The table of clinical toxicity grades modified from the National Cancer Institute Common Terminology Criteria for Adverse Events (NCI CTCAE) version 4.0 will be used in the grading of adverse events and laboratory abnormalities that are reported as adverse events.

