6.3.8 At end of treatment (49 days after last administration/infusion)

- Concomitant medications
- Assessment of all adverse events according to CTCAE 4.0
- Steroid intake

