- 3 Including serum creatinine, total bilirubin, ASAT, ALAT, alkaline phosphatase, phosphate, total protein, albumin, sodium, potassium, calcium and chloride
- 4 Pregnancy test must be done within 72 hours prior to randomization
- 5 ECG only day 1 of cycle 1 and 3, immediately after the ABT-414 infusion and only for patient treated with ABT-414 (Arm 1 or 2)
- 6 PK samples to be collected at day 1 of ABT-414 cycles 1, 2, 3 and then every 2 ABT-414 cycles (Day 5 samples will only be collected during cycles 1 and 2)
- 7 Hematology at day 21 can be omitted once treatment at the present dose level caused only grade 1 or less hem. toxicity at day 21 and only grade 2 or less at day 28
- 8 QoL only at week 8 and week 16 while on treatment
- 9 End of Treatment visits 35 days and 49 days after last protocol drug administration. PK samples to be drawn at 35 days after last protocol drug administration only.
- 10 If clinically indicated / if clinically relevant
- 11 Assessment of AEs not resolved after EOT or AEs related to study treatment
- 12 PD samples to be collected at day 1 of cycles 1, 2 and 3 and only for patient in an ABT-414 arm (Arm 1 or 2)
- 13 PG sample optional, to be collected at day 1 of cycle 1 or it may be collected anytime during the study
- 14 Repeat physical examination including WHO performance status and neurological evaluation, hematology, vital signs and adverse event assessments at day 28 for patients in the lomustine arm (Arm 3A)
- 15 Prophylactic steroid ophthalmic solution prior to each infusion of ABT-414; 2 drops in each eye every 8 hours to start 48 hours prior to ABT-414 dosing and continue for a total of 7 days

7 Criteria of evaluation

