7.2.1.6 Adverse Event Severity

The Investigator will rate the severity of each adverse event according to the National Cancer Institute Common Terminology Criteria for Adverse Events (NCI CTCAE Version 4.0). A copy of the CTCAE can be accessed from the CTEP home page (**Error! Hyperlink reference not valid.**<https://ctep.cancer.gov/>). NYHA criteria will be used for reporting congestive heart failure.

If a reported adverse event increases in severity, the initial adverse event should be given an outcome date and a new adverse event should be reported to reflect the change in severity.

The term "severe" is often used to describe the intensity (severity) of a specific event (as in mild, moderate or severe, or as described in CTC grades); the event itself, however, may be of relative minor medical significance (such as severe headache). This is not the same as "serious," which is based on patient/event outcome or action criteria usually associated with events that pose a threat to patient's life or functioning. Seriousness (not severity) serves as a guide for defining regulatory reporting obligations.

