7.2.1.8 Adverse Event Collection Period

All adverse events reported from the time of study drug administration until 49 days following discontinuation of study drug administration have elapsed will be collected, whether solicited or spontaneously reported by the subject.

In addition, serious and non-serious adverse events occurring after the subject signed the study-specific informed consent and prior to the initial dose of study drug will be collected only if they are considered by the Investigator to be causally related to required study procedures.

Adverse event information will be collected as shown below.

Adverse Event Collection

Protocol Related SAEs and Nonserious Adverse Events*	Serious and Nonserious Adverse Events Elicited and/or Spontaneously Reported		
Consent Signed	Study Drug Start	Study Drug Stopped	49 Days After Study Drug Stopped**

* Only if considered by the Investigator to be causally related to study-required procedures.

**If an AE/SAE occurs more than 49 days after study drug was stopped, it only needs to be reported if it is considered to have a reasonable possibility to be related to the protocol treatment or study participation.

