8.2.3.7 Safety and tolerability

In the SP:

The safety and tolerability analyses will be presented for the whole study duration. Severe grades (3/4) which did not resolve after treatment discontinuation or emerged during follow-up will be identified and listed. All forms up to the last safety assessment before progression or start of further anti-tumoral therapy will be used. There will be no formal comparison of safety endpoints. No p-value and confidence intervals will be carried out. Baseline laboratory and AE grades will not be accounted for in whole study duration safety analyses.

Laboratory and AE events occurring in patients who did not start their allocated treatment (ie excluded from SP) will be reported separately.

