This appendix will describe the evaluation of pharmacokinetics, safety and efficacy of ABT-414 in the pediatric HGG population, allowing access to a novel therapy for those who are in great need of better treatment options. Subjects < 18 years of age with pediatric HGG whose tumors demonstrate EGFR amplification will be assigned to this pediatric sub-study. Pediatric subjects will receive open-label ABT-414 at a dose of 1.0 mg/kg for subjects who are 6 to 17 years old (at the date of first ABT-414 dose), or 1.3 mg/kg for subjects who are 0 to 5 years old. These dosages are expected to produce pharmacokinetic drug exposures comparable to a 1.0 mg/kg dose in adults, the recommended starting dose for the adult portion of the study.

Objectives of the sub-study

The primary objectives will be the evaluation of safety, tolerability and pharmacokinetics of ABT-414 in a pediatric population < 18 years of age. The secondary objective will be to assess the effect of ABT-414 on tumor response per RANO (Response Assessment in Neuro-Oncology) criteria.

Primary Endpoints of the pediatric sub-study:

Safety including toxicities according to CTCAE criteria (Percentage of subjects with adverse events from subject's first visit until 49 days after the subject's last dose of study drug)

Pharmacokinetic parameters for ABT-414 and cys-mcMMAF (Maximum observed serum concentration (C_{max}) for ABT-414 and Cys-mcMMAF (toxin), half-life for ABT-414 and Cys-mcMMAF (toxin), and total drug exposure over time (AUC: Area Under the Curve) for ABT-414 and Cys-mcMMAF (toxin)

Secondary Endpoints of the pediatric sub-study:

Objective response rate, best response rate, and duration of response based on RANO criteria

Overall survival, Time to Progression, and Time to progression-free survival

Changes in neurological status and functioning (including PedsQL cancer module)

Exploratory Endpoints of the pediatric sub-study:

Assessment for tumor aberrations of H3.1, H3.3, BRAF, CDKN2A/B, IDH1, INI1, MGMT, PTEN.

Anti-drug antibodies

Methodology:

This is an uncontrolled, open-label, single-arm global study.

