15%	62.3%	76.8%	85.8%
20%	73.8%	86.6%	93.1%
25%	82.2%	92.5%	96.8%

All subjects who receive at least one dose of ABT-414 will be included in analyses. No interim analysis is planned.

Data Monitoring:

The EORTC and sponsor study teams will have open access to pediatric data throughout the study to inform the ongoing conduct of this open-label sub-study. EORTC will identify at least three individuals (a statistician, the PI, and a clinician from headquarters) that will review the safety events from the pediatric patients at the following timepoints: 4 weeks after each subject is enrolled and again at q4-6 month intervals while there are subjects that remain on therapy. If there are no subjects on active therapy, then the EORTC will not hold pediatric safety reviews.

Otherwise, data monitoring will be the same as specified for the adult population (refer to Chapter 9). Pediatric data will be analyzed separately from the adult study, but findings will be compared to those from the adult study. Pediatric data will not be included in the efficacy and safety analyses of the adult main study.

Translational research:

Tumor specimens will be collected where feasible for the same biomarker analyses that are planned for the adult population. Central molecular testing will include but not be limited to EGFR, H3.1, H3.3, BRAF, CDKN2A/B, IDH1, INI1, MGMT, PTEN. Insufficient tissue for Translational Research after EGFR amplification analysis will not prevent enrollment of the pediatric patients.

Forms and procedures for collecting data:

Data will be reported on the forms specifically designed by the EORTC Headquarters for this pediatric sub-study. Forms will be sent electronically to the EORTC Headquarters through the VISTA/RDC (Remote Data Capture System) as outlined in Chapter 14 of the adult protocol.

Informed consent:

Subjects and/or their legal guardians must be able to understand the risks and potential benefits and grant assent/consent to participate by signing a pediatric-specific informed assent/consent form(s) as per local and country specific laws and regulations.

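### The SAP's adverse-event tables stop 35 days after the last dose while the supplied protocol collects all adverse events to 49 days, so dated events from days 36–49 appear in no SAP adverse-event table

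*SAP*

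**What the plan says.** SAP section 11.1 makes treatment-emergent events the default for every AE summary. It defines them as events with onset or increased severity after the first dose "and no more than 35 days after the last dose of study drug (ABT-414/TMZ/lomustine". Nothing in sections 11.2 to 11.2.1.1 sets a longer window. The overview items in 11.2, including serious events, AESIs and events leading to death, are labelled treatment-emergent. Section 11.2.1.2 censors time to first AESI no later than 35 days after the last ABT-414 dose. Table 1, footnote 9, shows a single end-of-treatment visit at day 35, and the end-of-study rule in section 6.0 also uses 35 days.

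The supplied protocol works to a longer period. Under section 7.2.1.8, all AEs "until 49 days following discontinuation of study drug administration have elapsed will be collected"; only after that does reporting depend on relatedness. Section 6.3.8 is headed "At end of treatment (49 days after last administration/infusion" and includes assessment of all AEs. Footnote 9 to the table in section 6.5 confirms "End of Treatment visits 35 days and 49 days after last protocol drug administration". Section 8.5 sets the end-of-study condition at 49 days.

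On analysis, protocol section 8.2.3.7 covers the whole study duration, using forms up to the last safety assessment before progression or further anti-tumour therapy. It adds a listing: "Severe grades (3/4) which did not resolve after treatment discontinuation or emerged during follow-up will be identified and listed". Sections 8.2.3.7.3 to 8.2.3.7.5 plan worst-grade tables of all AEs, SAEs and related AEs without a 35-day limit.

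**The concern.** Under the supplied protocol, an AE with a known onset on days 36–49 is collected and assessed at a dedicated visit. The SAP then drops it from every AE table. Worsening is affected in the same way. Protocol section 7.2.1.6 closes the original record when severity increases, and "a new adverse event should be reported to reflect the change in severity". An event that starts by day 35 and worsens on days 36–49 is therefore tabulated only at its earlier, lower grade.

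What is at stake is the completeness of the descriptive safety profile: AE, SAE and AESI frequencies, the grade distribution, and the table of AEs leading to death. A treatment-emergent window shorter than the collection period is not wrong in itself. Here, however, the SAP gives no reason for it, and it differs from both the protocol's collection period and the protocol's own safety analysis section.

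**Working it through.** No sample size, power or alpha figure depends on this point. The check compares windows and then looks for any SAP output that closes the gap.

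1. **Size of the gap.** Inputs: 49 days (protocol 7.2.1.8) and 35 days (SAP 11.1). 49 − 35 = 14 days; 14/49 = 28.6% of the post-dose collection time.

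2. **The same gap against total observation time.** This needs an assumed treatment length. Take the design median PFS of 2.6 to 4.8 months (protocol 8.3) and the SAP's 30.4375 days per month.
   - 2.6 × 30.4375 = 79.1 days; 79.1 + 49 = 128.1; 14/128.1 = 10.9%.
   - 4.8 × 30.4375 = 146.1 days; 146.1 + 49 = 195.1; 14/195.1 = 7.2%.

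   On this assumption, 14 days is about 7–11% of treatment plus follow-up. Both shares are of time. Neither estimates events lost.

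3. **Whether days 36–49 are plainly remote from exposure.** Protocol section 1.6 gives an ABT-414 terminal half-life of about 7.5 to 12 days.
   - Day 35 is 35/12 = 2.9 to 35/7.5 = 4.7 half-lives after the last dose.
   - Day 49 is 49/12 = 4.1 to 49/7.5 = 6.5 half-lives after it.
   - A lomustine period is 42 days (protocol section 4), so the SAP window closes 42 − 35 = 7 days before a last lomustine period ends.

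   These figures do not fix a correct window. They show that the choice of 35 days needs a reason.

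4. **Search for a SAP output that covers days 36–49.**
   - Sections 11.2 to 11.2.1.1: none. The 11.1 default applies throughout.
   - Section 11.2.1.2: censored at 35 days at the latest.
   - Section 11.3: counts all deaths regardless of time, but this is not an AE table.
   - Section 11.4: grade 3–4 laboratory listings have no time limit, but these are laboratory values.
   - Section 11.1: AEs with an incomplete onset date are presumed treatment-emergent, so the gap concerns events with a known date.
   - Section 12: lists no different AE window for the EORTC analyses, although it allows that unlisted differences may exist.

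5. **SAP against the protocol's own analysis rule.** The protocol cuts off at progression or further anti-tumour therapy and has no fixed day limit. The SAP has a fixed limit of 35 days and no such cut-off in section 11. The SAP is therefore narrower for patients who stop without progression or new therapy, and wider, up to day 35, for those who progress.

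6. **Versions.** SAP section 3.0 says it follows protocol version 6, dated January 18, 2017. Appendix L of the supplied protocol refers to the implementation of version 7, so the supplied text is later. The version 6 AE window cannot be seen.

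**The case against.** The strongest reply is that a collection period is not an analysis window. A reader might infer that the protocol sets 49 days as the adult AE analysis window. It does not. Section 8.2.3.7 uses the whole study duration, cut off at progression or further therapy. Progression is also a reason to stop treatment (section 5.4), so for many patients the protocol's own tables would exclude days 36–49 too. This stands and limits the impact. It does not cover patients who stop for toxicity or refusal and remain on study without progression or new therapy.

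A reader might also infer that these events vanish from all reporting. That is too strong, because protocol sections 8.2.3.7.3 to 8.2.3.7.5 would tabulate them unless progression or new therapy came first. The point holds for SAP tables only.

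A third tempting step is the paediatric comparison. Appendix I defines its safety endpoint as "Percentage of subjects with adverse events from subject's first visit until 49 days after the subject's last dose of study drug" and says that "Pediatric data will be analyzed separately from the adult study, but findings will be compared to those from the adult study". From this one could argue that a 35-day adult window will be set against a 49-day paediatric one. The documents specify no comparison of AE rates, the paediatric analysis has a separate SAP that was not supplied, and that endpoint starts at the first visit, not the first dose. All that follows is that any such comparison should use a common window.

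Finally, the SAP uses 35 days consistently, which suggests it followed its parent version, and some adults may have finished follow-up before 49-day collection applied. This is plausible and cannot be checked. It explains the mismatch without removing it. The SAP also plans no p-values or confidence intervals for safety, and no efficacy conclusion depends on this.

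**Conclusion.** The mismatch is confirmed in the text. Followed as written, the SAP leaves AEs, SAEs and AESIs with a known onset or worsening on days 36–49 out of all its AE tables. It also omits the follow-up listing of grade 3/4 events that the protocol plans. The gap is 14 days, or 28.6% of the post-dose collection time.

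The conclusion rests on the supplied protocol text and is limited to SAP tables. It applies to patients actually followed under 49-day collection, whose number is unknown. How many events are affected, and whether any between-arm impression would change, cannot be determined from the documents. Version lag is the likely explanation but remains an inference.

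**What to change.** Preferred: set the upper limit of the treatment-emergent definition (SAP 11.1) and the AESI censoring (SAP 11.2.1.2) to the protocol's 49-day collection period, and show the 35-day tables alongside.

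Alternative: keep 35 days, state why, and add by-arm AE, SAE and AESI tables for onset or worsening on days 36–49.

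In either case:
- add the follow-up listing of grade 3/4 events from protocol 8.2.3.7;
- state how the chosen window relates to that section's cut-off at progression or further therapy;
- reconcile SAP Table 1, footnote 9, and the SAP end-of-study rule with the protocol's 49 days;
- use a common window for any comparison of adult and paediatric AEs.

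The cost is SAP wording, one more set of tables and one listing. AE counts may rise slightly. Ascertainment on days 36–49 may be uneven across protocol versions, which is why the 35-day and later results should both be visible.
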